7.6. Performance Status Assessments

[figure not shown]
7.6.1. ECOG Performance Status

[figure not shown]
ECOG performance status ([Oken et al 1982](#); [Table 12](#)) will be required at screening to evaluate eligibility and will be assessed at other study visits per [Table 8](#). Performance status must be assessed by a medically qualified individual and recorded in the eCRF.

Table 12: ECOG Performance Scores

Grade	Performance Status
0	Fully active, able to carry on all predisease performance without restriction.
1	Restricted in physically strenuous activity but ambulatory and able to carry out work of a light or sedentary nature, eg, light house work, office work.
2	Ambulatory and capable of all self-care but unable to carry out any work activities. Up and about more than 50% of waking hours.
3	Capable of only limited self-care, confined to bed or chair more than 50% of waking hours.
4	Completely disabled. Cannot carry on any self-care. Totally confined to bed or chair.
5	Dead.

7.9. Other Study Procedures

7.9.1. Distribution of Subject Reminder Cards

Subjects will be provided with a reminder card at each visit. The subject reminder card will indicate the date/time of the next visit and will also remind the subject that they should not take their morning dose of study drug on Day 1, Day 8, and Day 15, as they will take it after blood draws have been completed for safety evaluation. The reminder cards for the Day 1, 8, and 15 visits will have an area on which the date and time of the last dose taken (from the previous evening) and the time of their last meal before the visit should be recorded.

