1.3. Potential Risks and Benefits of the Treatment Regimen

1.3.1. INCB039110

As of 13 DEC 2016, 9 Phase 1, 4 Phase 1/2, and 5 Phase 2 clinical studies with INCB039110, including studies of INCB039110 in combination with chemotherapeutic agents, corticosteroids, pembrolizumab (anti-programmed cell death 1 monoclonal antibody), and investigational PI3K δ (INCB040093 and INCB050465) and indoleamine 2,3-dioxygenase 1 (epacadostat) inhibitors, have either been completed or are ongoing. A total of 777 subjects were enrolled in these studies and received at least 1 dose of INCB039110. In completed clinical pharmacology studies, INCB039110 has been administered to 197 healthy adult subjects as a single dose, repeat single doses, or multiple doses for up to 10 days.

In the ongoing and completed clinical pharmacology studies, INCB039110 was generally safe and well tolerated in healthy subjects, with few discontinuations. The majority of treatment-emergent adverse events (TEAEs) were mild in severity. There have been no clinically significant, unanticipated safety findings or trends observed. The main drug effect identified was a rapidly reversible dose related decrease in neutrophil counts presumably caused by neutrophil margination; neutrophil decreases generally resolved within 24 to 48 hours of dose discontinuation. Other reversible hematologic abnormalities, including decreased reticulocyte count, were observed after multiple-dose administration of higher dose levels at which JAK2 inhibition was noted.

Adverse events (AEs) that have been reported by more than 5% of healthy subjects in an individual study receiving INCB039110 included fatigue, headache, neutropenia, nausea, contact dermatitis, ecchymosis, reticulocyte count decreased, excoriation, and nasal congestion. Adverse events reported by more than 10% of subjects receiving INCB039110 in the psoriasis study included nasopharyngitis. Adverse events reported by more than 10% of subjects in the MF study included fatigue, thrombocytopenia, nausea, diarrhea, upper respiratory tract infection, constipation, cough, dyspnea, peripheral edema, pyrexia, dizziness, abdominal pain, night sweats, pain in extremity, arthralgia, contusion, headache, pruritus, vomiting, and increased bilirubin/hyperbilirubinemia. In the RA study, there were no TEAEs reported by more than 10% of subjects.

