5.2. INCB039110

5.2.1. Description and Administration

INCB039110 drug substance is a white to off-white powder. INCB039110 100 mg (free base equivalent) sustained release tablets (SR3 formulation) contain the active ingredient, hypromellose, microcrystalline cellulose, lactose monohydrate, and magnesium stearate.

In Phase 1, INCB039110 tablets will be administered orally (PO) at the cohort-specific dose (eg, 3 × 100 mg tablets) QD. In Phase 2, INCB039110 tablets will be administered PO at the RP2D identified in Phase 1. The use of strong CYP3A inhibitors/inducers, grapefruit, and pomegranate should be avoided for the duration of the study ([Appendix B](#)).

Due to the potential for WBC margination, blood samples should be collected before study treatment administration at all applicable study visits.

Subjects may have dose reductions of INCB039110 during the course of treatment based on AEs, clinical evaluation, and laboratory assessments. See Section [5.5.1](#) for INCB039110 dose modification guidance.

Subjects are permitted to remain on INCB039110 until withdrawal from study treatment is considered necessary as per Section [5.6](#).

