6. STUDY ASSESSMENTS

All study assessments will be performed as indicated in the schedule of assessments in [Table 8](#); the order of assessments is suggested by the order of mention within the schedule. Laboratory assessments are shown in [Table 9](#).

Table 8: Schedule of Assessments

Procedure	Section	Screening	Treatment				EOT	Follow-Up	Comments
		Day -28 to -1	Day 1	Day 8 (± 3 days)	Day 15 (± 3 days)	Day 28/Q28D (± 3 days)		EOT + 30-35 Days	
Informed consent	7.1	X							
Contact IVRS	7.2	X	X			X	X		
Inclusion and exclusion criteria	3.1 3.2	X	X						
Demography and medical history	7.3.1	X							
Prior/concomitant medications	7.3.2	X	X	X	X	X	X	X	
Physical exam/ weight/height	7.4.2 7.4.3	X*	X	X	X	X	X	X	*Comprehensive exam at screening; targeted physical exam thereafter. Height required at screening only.
Vital signs	7.4.4	X	X	X	X	X	X	X	
12-lead ECG	7.4.5	X*	X*	X**					*Triplicate ECGs will be performed during screening and on Day 1 before starting study treatment. **Triplicate ECGs will be performed predose and 2 hours (± 15 minutes) after receiving INCB039110 on Day 8. Additional ECGs may be performed as clinically indicated.
ECOG status	7.6.1	X	X			X	X	X	
AE assessment	7.4.1	X	X	X	X	X	X	X	
CT or MRI	7.5.1	X				X*	X		*Week 8, Week 16, and then every 16 weeks ± 1 week. Also required to confirm CR.
FDG-PET scan/PET-CT	7.5.2	X				X*			*Required at baseline and to confirm CR or if clinically indicated.

Table 8: Schedule of Assessments (Continued)

Procedure	Section	Screening	Treatment				EOT	Follow-Up	Comments
		Day -28 to -1	Day 1	Day 8 (± 3 days)	Day 15 (± 3 days)	Day 28/Q28D (± 3 days)		EOT + 30-35 Days	
Bone marrow exam	7.5.3	X*							*Required as a screening assessment unless performed as per standard of care within 60 days of Day 1. Repeat to confirm CR or if clinically indicated.
Dispense study drug	5.1		X			X			
Study drug accountability	5.4		X	X	X	X	X		
INCB039110 administration	5.2.1		X*	X*	X*	X*			*Subjects should refrain from taking INCB039110 on clinic visit days until after local laboratory blood samples are collected.
Ibrutinib administration	5.3.1		X*	X*	X*	X*			*Subjects should refrain from taking ibrutinib on clinic visit days until after local laboratory blood samples are collected.

FDG = fluorodeoxyglucose; PET = positron emission tomography.

Table 9: Laboratory Assessments

Laboratory Tests	Section	Screen	Day 1	Day 8 (± 3 days)	Day 15 (± 3 days)	Day 28/Q28D (± 3 days)	EOT	Follow-Up	Details
Local Laboratory Samples									

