Serum chemistries	7.4.6.1	X	X		X	X	X	X	Day 1 laboratory tests may be omitted if the screening tests occurred in preceding 7 days. All lab draws should be performed before dose administration.
Hematology	7.4.6.2	X	X	X	X	X	X	X	Day 1 laboratory tests may be omitted if the screening tests occurred in preceding 7 days. All lab draws should be performed before dose administration.
Coagulation panel	7.4.6.2	X	X			X*	X		Day 1 laboratory tests may be omitted if the screening tests occurred in preceding 7 days. All lab draws should be performed before dose administration. *After Day 28, should be repeated every 3 months, ie., Day 112, Day 196, etc.
Serology	7.4.6.5	X							
Serum pregnancy	7.4.6.4	X					X		All female subjects of childbearing potential; negative pregnancy test must be obtained within 7 days of first dose of study treatment.
Urine pregnancy	7.4.6.4				X				Only as medically indicated for females of childbearing potential.

Table 10: Table of Required Laboratory Analytes

Serum Chemistries	Serology	Hematology	Coagulation
Albumin	HBsAg	Hemoglobin	PT
Alkaline phosphatase	Anti-HBsAg	Hematocrit	PTT
ALT	Anti-HB core IgG	Platelet count	aPTT
AST	HCV antibody	Red blood cell count	INR
Bicarbonate	HCV-RNA	White blood cell count	
Blood Urea Nitrogen	HBV-DNA	Differential cell count:	
Calcium		Basophils	
Chloride		Eosinophils	
Creatinine		Lymphocytes (absolute)	
Glucose		Monocytes	
LDH		Neutrophils (absolute)	
Phosphate			
Potassium			
Sodium			
Total bilirubin ^a			
Direct bilirubin ^a			
Indirect bilirubin			
Total serum protein			
Total cholesterol			
CRP			

CRP = C-reactive protein.

^a Only required if total bilirubin is elevated.

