7.4.6. Laboratory Assessments

Blood draws for laboratory assessments will occur at study visits indicated in [Table 9](#). Blood draws will be completed before the subject receives the morning dose of INCB039110. Specific laboratory assessments are listed in [Table 10](#). The screening portion of the study will require a maximum of 16 mL of blood, the first 28 days on study will require a maximum of 35 mL of blood, and each subsequent 28 days on study will require a maximum of 11 mL of blood for local safety laboratory assessments.

All laboratory assessments will be performed at a local laboratory using institutional best practices. Results and normal reference ranges will be entered into the eCRF.

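### The subject reminder card holds the morning dose only on Days 1, 8 and 15, while the protocol's laboratory rules call for predose blood at every on-treatment laboratory visit, including Day 28 and every 28 days after

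*Protocol*

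**What the plan says.** Protocol Section 7.9.1 provides a reminder card at each visit. The card gives the time of the next visit and reminds subjects that "they should not take their morning dose of study drug on Day 1, Day 8, and Day 15". The stated reason is "as they will take it after blood draws have been completed for safety evaluation". The cards for those three visits also have a space for the date and time of the last dose, described as taken the evening before, and for the last meal.

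The rest of the protocol sets the timing of blood draws more broadly:

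- **Table 8** marks administration of both drugs at Day 1, Day 8, Day 15 and Day 28/Q28D, with the note "Subjects should refrain from taking INCB039110 on clinic visit days until after local laboratory blood samples are collected". Ibrutinib has a matching note.
- **Table 9** schedules hematology at the same visits, plus end of treatment and follow-up, and adds "All lab draws should be performed before dose administration".
- **Section 5.2.1**: "Due to the potential for WBC margination, blood samples should be collected before study treatment administration at all applicable study visits".
- **Section 7.4.6**: "Blood draws will be completed before the subject receives the morning dose of INCB039110". Section 7.4.6.2 repeats this for hematology.
- **Section 1.3.1** asks for hematology before dosing because INCB039110 can lower the ANC transiently. It reports that "neutrophil decreases generally resolved within 24 to 48 hours of dose discontinuation".

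**The concern.** The card is the reminder that the subject takes home, and dosing is oral and once daily. A subject who reads a list of three days may take the dose at home before a visit that is not on the list. At those visits the ANC could then be drawn after the dose, when the plan intends it to be drawn before.

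Two uses of the ANC are exposed:

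- **Interruption guidelines (protocol Table 4).** An ANC of 1.0 × 10⁹/L or lower leads to interruption of INCB039110. A Grade 4 ANC leads to interruption and, if judged related to INCB039110, restart at the next lower level. Margination is a drug effect, so such a fall could be judged related.
- **Laboratory summaries.** SAP Section 8.3.2 uses all postbaseline values for the worst-value shift tables. SAP Table 4 picks records for by-visit summaries on scheduled status, laboratory and visit window. Neither considers whether the sample was drawn before the dose.

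**Working it through.** The plan states no figure to reproduce here. The check is a comparison of texts and a visit count.

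**Step 1. Which visits each text names**

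| Source | Day 1 | Day 8 | Day 15 | Day 28 and every 28 days |
|---|---|---|---|---|
| Reminder card, Section 7.9.1 | named | named | named | not named |
| Table 8, dosing notes | covered | covered | covered | covered |
| Table 9, hematology | covered | covered | covered | covered |
| Sections 1.3.1, 5.2.1 | all applicable visits | same | same | same |
| Sections 7.4.6, 7.4.6.2 | all laboratory draws | same | same | same |

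The card is the only text with the shorter list. Its reason, safety blood draws, applies equally to the visits it omits.

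**Step 2. Visit count**

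Inputs:

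- Treatment lasts about 4 months (protocol Synopsis, estimated duration of participation).
- Visits follow Table 9: Days 1, 8, 15, 28 and every 28 days. The coagulation note in Table 9, which gives Days 112 and 196 as repeat days, confirms that later visits fall on multiples of 28.

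Count:

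- 28-day visits: 28 × 1, 2, 3, 4 = Days 28, 56, 84 and 112, so 4 visits.
- All scheduled hematology visits: 3 + 4 = 7.
- Day 1 precedes the first dose and cannot show margination. Visits after the first dose: 7 − 1 = 6.
- Named on the card: Days 8 and 15, so 2 of 6 (33%).
- Not named: 4 of 6 (67%).

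For a subject treated through k visits of the 28-day series, the share not named is k / (k + 2). Treatment length varies between subjects, so taking k as an assumption:

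| k | Last visit | Share not named |
|---|---|---|
| 1 | Day 28 | 1/3 = 33% |
| 2 | Day 56 | 2/4 = 50% |
| 4 | Day 112 | 4/6 = 67% |
| 6 | Day 168 | 6/8 = 75% |

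**Step 3. Can a false DLT follow?**

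- Protocol Table 7 counts Grade 4 neutropenia only if it fails to recover to Grade 2 or better within 3 days of interrupting drug. Its note gives margination as the reason.
- Section 5.5.2 also excludes laboratory abnormalities of 72 hours or less without clinically significant signs or symptoms.
- Febrile neutropenia has no persistence step of its own, but it needs fever as well as a low count.
- The Day 28 visit has a window of ±3 days (Day 25 to Day 31), so it may fall after the DLT period has closed.

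A single low ANC drawn after the dose is therefore unlikely to become a DLT.

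**Step 4. Can the effect on ANC be sized?**

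No. The documents give neither the depth of the ANC fall at a given time after dosing nor a rate of post-dose draws. Recovery takes 24 to 48 hours after stopping, and a predose sample on once-daily dosing comes about 24 hours after the last dose, so it may still carry part of the effect. Predose sampling makes the timing consistent. It does not guarantee a value free of margination.

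**The case against.** The strongest reply is that the operative sections agree with one another and that sites work from the schedule, not from the card. The card is silent about Day 28; it does not tell anyone to dose at home. A post-dose sample needs two failures: the subject treats the list as complete, and the site does not apply Tables 8 and 9. This stands, and it makes the consequence a risk and not a certainty.

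Protocol Table 4 is also described as guidelines, applied with clinical judgment and medical monitor input. Transient values of 72 hours or less without clinically significant signs or symptoms may be exempt from dose reduction, and the first ANC row restarts at the same dose. This stands too, and limits the effect on dosing.

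Parts of the sampling text are blacked out, so Days 1, 8 and 15 might have been chosen for samples that cannot be seen. That could explain the dose-time and meal-time fields. It does not explain the short list for the hold, because the card itself gives safety evaluation as the reason.

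A reader might infer more than the documents support:

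- **That Phase 1 dose selection is compromised through the Day 28 ANC.** The persistence and transient-value rules make this unlikely.
- **That the neutropenia tables will be inflated, or change from baseline biased, by a known amount.** No effect size is given. Baseline precedes all drug, so even a predose on-treatment value may differ from it because of margination.
- **That 4 of 6 is an error rate.** It counts visits that the card does not name, not samples drawn late.

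**Conclusion.** The inconsistency is real. The card as specified does not carry the plan's own predose rule to Day 28 and later visits: 4 of the 6 hematology visits after the first dose over about 4 months, assuming the Table 9 schedule and the Synopsis estimate of treatment length. The plausible result is mixed ANC sampling times, which could affect the Table 4 interruption triggers and the worst-grade and shift tables. This depends on subjects relying on the card and on sites not correcting it, and its size cannot be computed. The Phase 2 primary endpoint, ORR, is not touched. The wording about a dose taken the evening before, set against a once-daily morning dose, is a smaller inconsistency in the same section. The point merits correction because it is easily fixed, not because it threatens the trial's conclusions.

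**What to change.** Reconcile Section 7.9.1 with Tables 8 and 9 and Sections 5.2.1 and 7.4.6, so that the reminder card and the laboratory timing rule name the same visits. In the same edit, reconcile the card's reference to a dose the evening before with the morning-dose wording in Sections 7.4.6 and 7.9.1. Which text governs is for the sponsor to settle.

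The cost is one or two protocol sentences and a revised card, with no added visit or sample.

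As an optional addition, a yes/no eCRF field could record whether each hematology sample was drawn before that day's dose. Any post-dose values could then be identified in the ANC summaries. The reconciliation does not depend on it.

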8. SAFETY MONITORING AND REPORTING

8.1. Adverse Events

8.1.1. Definitions

For the purposes of this Protocol, an adverse event (AE) is defined as any untoward medical occurrence associated with the use of a drug in humans, whether or not considered drug related, that occurs after a subject provides informed consent. Abnormal laboratory values or test results occurring after informed consent constitute AEs only if they induce clinical signs or symptoms, are considered clinically meaningful, require therapy (eg, hematologic abnormality that requires transfusion), or require changes in the study drug(s).

8.1.2. Reporting

Adverse events that begin or worsen after informed consent should be recorded on the Adverse Events form of the eCRF. Conditions that were already present at the time of informed consent should be recorded on the Medical History form in the eCRF. Monitoring for the occurrence of new AEs should be continued for at least 30 days after the last dose of study drug. Adverse events (including laboratory abnormalities that constitute AEs) should be described using a diagnosis whenever possible rather than by individual underlying signs and symptoms. When a clear diagnosis cannot be identified, each sign or symptom should be reported as a separate AE.

The term "disease progression" should be recorded as an AE/SAE only if there are no other identifiable AEs/SAEs associated with the disease progression at the time of reporting. For events associated with disease progression, the relevant signs and symptoms should be reported using a diagnosis whenever possible rather than individual underlying signs and symptoms. When a clear diagnosis cannot be identified, each sign or symptom should be reported as a separate AE. If the events resulting from disease progression meet the criteria for an SAE (eg, resulted in hospitalization, a life-threatening event, or death), the specific event(s) should be reported as an SAE(s) as described in Section 8.3.2. In both cases (ie, AEs or SAEs related to disease progression), it should be indicated that each event (reported as a diagnosis or as signs and symptoms) is related to disease progression on the Adverse Events form of the eCRF.

The severity of AEs will be assessed using CTCAE v4.03 Grades 1 through 4. The CTCAE v4.03 severity of Grade 5 will not be used; AEs resulting in death will be graded accordingly using Grades 1 through 4 and have the outcome noted as fatal. If an event is not classified by CTCAE, the severity of the AE will be graded according to the scale below to estimate the grade of severity.

Grade 1	Mild; asymptomatic or mild symptoms; clinical or diagnostic observations only; intervention not indicated.
Grade 2	Moderate; minimal, local, or noninvasive intervention indicated; limiting age-appropriate activities of daily living.
Grade 3	Severe or medically significant but not immediately life-threatening; hospitalization or prolongation of hospitalization indicated; disabling; limiting self-care activities of daily living.
Grade 4	Life-threatening consequences; urgent intervention indicated.

The occurrence of AEs should be sought by nondirective questioning of the subject during the screening process after signing the ICF and at each visit during the study. Adverse events may also be detected when they are volunteered by the subject during the screening process or between visits, or through physical examination, laboratory test, or other assessments. To the extent possible, each AE should be evaluated to determine:

- The severity grade (CTCAE Grade 1 to 4).
- Whether there is at least a reasonable possibility that the AE is related to the study treatment: suspected (yes) or not suspected (no).
- The start and end dates, unless unresolved at final follow-up.
- The action taken with regard to study drug.
- The event outcome (eg, not recovered/not resolved, recovered/resolved, recovering/resolving, recovered/resolved with sequelae, fatal, unknown).
- The seriousness, as per serious adverse event (SAE) definition provided in Section 8.3.1.

Unlike routine safety assessments, SAEs are monitored continuously and have special reporting requirements (see Section 8.3.2).

All AEs should be treated appropriately. If an AE is treated with a concomitant medication or nondrug therapy, this action should be recorded on Adverse Event form and the treatment should be specified on the Prior/Concomitant Medications or Procedures and Non-Drug Therapy form in the eCRF.

Once an AE is detected, it should be followed until it has resolved or until it is judged to be permanent; assessment should be made at each visit (or more frequently if necessary) of any changes in severity, the suspected relationship to the study drug, the interventions required to treat the event, and the outcome.

When the severity of an AE changes over time for a reporting period (eg, between visits), each change in severity will be reported as a separate AE until the event resolves. For example, 2 separate AEs will be reported if a subject has Grade 1 diarrhea, meeting the definition of an AE that lasts for 3 days before worsening to a Grade 3 severity. The Grade 1 event will be reported as an AE with a start date equal to the day the event met the Grade 1 AE definition and a stop date equal to the day that the event increased in severity from Grade 1 to Grade 3. The Grade 3 event will also be reported as an AE, with the start date equal to the day the event changed in

intensity from Grade 1 to Grade 3 and a stop date equal to the day that the event either changed severity again or resolved.

